* Only one treatment period (Visit 2) for dose groups 1-7 and 10. Two identical treatment periods separated by a wash-out phase of at least 14 days between drug administration for dose group (DG) 8 (Visit 2) and DG 9 (Visit 3). In DGs 8-9 the same subjects will be included.

1. Subject must be informed and written informed consent obtained prior to starting any screening procedures. Screening procedures include physical examination, check of vital signs, ECG (including rhythm strip of at least 15 minutes), safety laboratory (including drug screening), demographics (including determination of body height and weight, smoking status and alcohol history), relevant medical history, concomitant therapy and review of inclusion/exclusion criteria. Pharmacogenetic samples will be collected if needed.
2. The time is approximate; the respective procedure is to be performed and completed within 3 h prior to drug administration. Allocation to treatment may be performed at any time following enrolment but must be completed prior to (first) drug administration.
3. If several actions are indicated at the same time point, the intake of meals will be the last action.
4. End of trial examination includes physical examination, vital signs, ECG, safety laboratory, recording of AEs and concomitant therapies.
5. Only urine drug screening and alcohol breath test will be done at this time point.
6. AEs and concomitant therapies will be recorded throughout the trial, but will be specifically asked for at the time points indicated in the Flow Chart above.

Proprietary confidential information © 2017 Boehringer Ingelheim International GmbH or one or more of its affiliated companies

7. Safety laboratory to be taken and to be medically evaluated within 3 days prior to administration of study drug; this ambulatory visit including the safety laboratory can be omitted, if the screening examination is performed on Days -3, -2 or -1.
8. Two blood sample for stability testing will be taken at this time point (refer to Section [5.5.2.4](#))
9. The ECG recording has to be performed as triple at this time point
10. Sampling times and periods may be adapted based on information obtained during the trial (e.g. preliminary PK data) including addition of samples and visits as long as the total blood volume taken does not exceed 500 mL per subject
11. Including blood sample for metabolite identification (refer to Section [5.5.2.2](#))

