3.2 DISCUSSION OF TRIAL DESIGN, INCLUDING THE CHOICE OF CONTROL GROUP

For single-rising dose trials, the design described in Section [3.1](#) is viewed favourable under the provision not to expose the subjects involved to undue risks since the main study objective is to investigate safety and tolerability of BI 730357 and the risk to subjects will be minimized by studying sequentially ascending doses. For safety reasons the first cohort of each dose level will be treated in a fixed treatment sequence (Active-Placebo-Active-Active). The dose level being investigated at any time will be known to subjects, but single-blind conditions regarding each subject's treatment (active or placebo) will be maintained for both cohorts of each dose level.

The disadvantage of this trial design is a possible observer bias with regard to the dose-depending effects as well as time effects, but it has the virtue of minimizing subject risk by sequentially studying ascending doses. As time-effects are expected to be small relative to the differences between the doses in the broad range investigated, unbiased comparisons between treatments can still be expected.

It is standard in trials involving healthy volunteers to include a placebo group as control for the evaluation of safety and tolerability. Each dose group consists of 8 subjects with 6 on active treatment, and 2 on placebo. The placebo control group includes all subjects of all dose groups treated with placebo. 6 subjects per active treatment group are in general considered as sufficient for the exploratory evaluation of pharmacokinetics.

For the BA part comparing bioavailability of BI 730357 following administration as tablet in the fasted state versus oral solution (PfOS) in fasted state as well as tablet in the fasted state versus tablet under fed conditions, the crossover design is viewed favourable due to its efficiency: since each subject serves as his own control, the comparison between the treatments is based on a comparison within subjects rather than between subjects. Thus the inter-subject variability is removed from the comparison between treatments [\[R94-1529\]](#). Blinding is not possible because the treatments are distinguishable.

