6.2.2 Treatment periods

Study participants will be admitted to trial site at least 1 hour prior to administration of the trial medication. They will be kept under close medical surveillance for at least 24 hours following drug administration. Thereafter the subjects will be allowed to leave the trial site after formal assessment and confirmation of their fitness. Afterwards the study will be performed in an ambulatory fashion until the end-of-study examination.

For DGs 1-7 and 10 of the SRD part, each subject will receive one dose of the respective trial medication (BI 730357 or placebo) at visit 2. In DGs 8 and 9 of the SRD part, the same subjects will be included and each subject will be treated with the same trial medication (either always active or always placebo), i.e. they will receive the respective trial medication at first in DG 8 (Visit 2) following a standard continental breakfast and in DG 9 (Visit 3) following a high-fat breakfast. The treatments of DG 8 and DG 9 are separated by a wash-out phase of at least 14 days between each drug administration.

The participants of the BA part will receive the respective trial medication (BI 730357) at visit 2, 3 and 4. Details on treatments and procedures of administration are described in Section [4.1.4](#).

For details on time points and procedures for collection of plasma and urine samples for PK analysis, refer to [Flow Chart](#) and Section [5.5.2](#).

The safety measurements performed during the treatment period are specified in Section [5.2](#) of this protocol and in the Flow Chart. For details on time points for all other trial procedures, refer to the Flow Chart. AEs and concomitant therapy will be assessed continuously from screening until the end of trial examination.

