2. LIST OF ABBREVIATIONS

Term	Definition / description
ADS	Analysis Dataset
AE	Adverse Event
AESI	Adverse Event of Special Interest
ALT	Alanine Aminotransferase
ANCOVA	Analysis of Covariance
ANOVA	Analysis of Variance
AST	Aspartate Aminotransferase
AUC _{0-∞}	Area under the concentration-time curve of the analyte in plasma over the time interval from 0 extrapolated to infinity
BA	Bioavailability
BI	Boehringer Ingelheim
BLQ	Below The Lower Limit Of Quantification
BMI	Body Mass Index
BWC	Bioavailability/Bioequivalence, Within-Subject Design, Time-Controlled
BWU	Bioavailability/Bioequivalence, Within-Subject Design, Time-Uncontrolled
CARE	Clinical Data Analysis and Reporting Environment
CI	Confidence Interval
Cmax	Maximum measured concentration of the analyte in plasma
CTP	Clinical Trial Protocol
CTR	Clinical Trial Report
CV	Arithmetic Coefficient of Variation
DB	Dose Proportionality, Between-Subject Design
DBLM	Database Lock Meeting
DG	Dose Group
ECG	Electrocardiogram
ECGPKS	ECG PK Set
eCRF	Electronic Case Report Form
EudraCT	European Union Drug Regulating Authorities Clinical Trials
gCV	Geometric Coefficient of Variation
gMean	Geometric Mean
HR	Heart Rate

Term	Definition / description
ICH	International Conference On Harmonisation
██████████	██████████
LLT	Lower Level Term
Max	Maximum
mRNA	Messenger Ribonucleic Acid
Mean	Arithmetic Mean
MedDRA	Medical Dictionary For Regulatory Activities
Min	Minimum
N	Number non-missing Observations
NC	Not Calculated
NOA	Not Analysed
NOP	No Peak Detectable
NOR	No Valid Result
NOS	No Sample Available
O*C	Oracle Clinical
PD	Pharmacodynamic(s)
PDS	Pharmacodynamic Set
PfOS	Powder For Oral Solution
PK	Pharmacokinetic(s)
PKS	PK Parameter Analysis Set
po	per oral
POC	Percent Of Control
PR	Pulse Rate
PT	Preferred Term
PV	Protocol Violation
qd	Quaque Die, Once Daily
QT	Time between start of the Q-wave and the end of the T-wave in an electrocardiogram
QTc	QT interval corrected for heart rate using the method of Fridericia (QTcF) or Bazett (QTcB)
R	Reference Treatment
RAGe	Report Appendix Generator system
REP	Residual Effect Period

Term	Definition / description
RPM	Report Planning Meeting
RS	Randomised Set
SAS®	Statistical Analysis System
SD	Standard Deviation
SOC	System Organ Class
SP	Sampling Point
SRD	Single Rising Dose
T	Treatment
T1/T2	Test treatment 1/2
Tb	Tablet
TS	Treated Set
TSAP	Trial Statistical Analysis Plan
ULN	Upper Limit of Normal
WHO-DD	World Health Organization Drug Dictionary

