6. GENERAL ANALYSIS DEFINITIONS

6.1 TREATMENTS

SRD part:

In total, it was planned to include 72 healthy male volunteers in the SRD part of this trial. Each of the 10 sequential groups includes 8 subjects (6 active, 2 placebo) and is divided into two cohorts. The first cohort will be treated in a fixed sequence and the second cohort will be randomised.

In dose groups (DG) 1-7 and 10 each subject will receive one oral dose of BI 730357 or Placebo respectively at Visit 2, Day 1.

In DG 8 (400 mg/placebo with continental breakfast; Visit 2, Day 1) and DG 9 (400 mg/placebo with high-fat breakfast; Visit 3, Day 1) the same subjects will be included and treated with the same treatments (i.e. always with active or with placebo) for an intra-individual comparison of the two different diets (after washout period of at least 14 days).

BA part:

In total, it was planned to include 12 healthy male volunteers in the BA part of this trial. Each subject will receive BI 730357 as tablet (Tb) in a fasting state (reference treatment R), as oral solution (PfOS) in a fasting state (test treatment T1) and as tablet after a standardised high fat breakfast (test treatment T2) in an open label, randomised manner.

For details of dosage and formulation see [Table 6.1: 1](#) and [Table 6.1: 2](#) below.

Table 6.1: 1 Labels for treatments for use in the CTR (SRD Part)

Dose group	Treatment		Short label
1-10	M/N/U/V	Placebo solution / tablet, po, qd	Placebo total
1-7	M/N	Placebo solution / tablet, po, qd	Placebo fast
8	U	Placebo tablet, po, qd, fed continental	Placebo fed1
9-10	V	Placebo tablet, po, qd, fed high-fat	Placebo fed2
8-10	UV*	Placebo tablet, po, qd, fed continental/high-fat	Placebo fed
1	A	BI 730357, 1 mg/mL solution, 2 mg, po, qd	2mg PfOS fast
2	B	BI 730357, 1 mg/mL solution, 8 mg, po, qd	8mg PfOS fast
3	C	BI 730357, tablet, 25 mg, qd	25mg Tb fast
4	D	BI 730357, tablet, 50 mg, qd	50mg Tb fast
5	E	BI 730357, tablet, 2*50 mg, qd	100mg Tb fast
6	F	BI 730357, tablet, 4*50 mg, qd	200mg Tb fast
7	G	BI 730357, tablet, 8*50 mg, qd	400mg Tb fast
8	S	BI 730357, tablet, 8*50 mg, qd, fed continental	400mg Tb fed1
9	T	BI 730357, tablet, 8*50 mg, qd, fed high-fat	400mg Tb fed2
8-9	ST*	BI 730357, tablet, 8*50 mg, qd, fed continental/high-fat	400mg Tb fed
10	K	BI 730357, tablet, 16*50 mg, qd, fed high-fat	800mg Tb fed2

fed1 means intake of standard continental breakfast prior to drug administration

fed2 means intake of standard high-fat breakfast prior to drug administration

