fed means intake of either standard continental or standard high-fat breakfast prior to drug administration

*: Placebo fed / 400mg Tb fed will be included in the same analyses in which within the BA part only the total group would be displayed, otherwise Placebo fed / 400mg Tb fed will be split into fed1 for subjects with continental breakfast and fed2 for subjects with high-fat breakfast

CTP: *The placebo control group in the safety evaluation will consist of all placebo treated subject, regardless of the dose group in which they were treated.*

This is applicable to the placebo control groups total, fast, fed1, fed2 and fed.

Table 6.1: 2 Labels for treatments for use in the CTR (BA Part)

Treatment		Short label
X (R)	BI 730357, tablet, 25 mg, fasted, qd	25mg Tb fast
Y (T2)	BI 730357, tablet, 25 mg, fed high-fat, qd	25mg Tb fed2
Z (T1)	BI 730357, 10 mg/mL solution, 25 mg, fasted, po, qd	25mg PfOS fast

Table 6.1: 3 Overview of treatments for intra-individual comparison

Study part	Test treatment (T)	Reference treatment (R)
SRD	400mg Tb fed2	400mg Tb fed1
BA	25mg PfOS fast (T1)	25mg Tb fast (R)
	25mg Tb fed2 (T2)	25mg Tb fast (R)

The following separate study phases will be defined for the analyses of AEs:

- **Screening** (ranging from 0:00 h on day of informed consent until administration time of study drug)
- **On-treatment**
SRD part:
DGs 1-7, 10: ranging from administration time of study drug until end of trial-termination date
DG 8 and 9: separately for each treatment, ranging from administration time of study drug until administration time of next study drug dose or end of trial-termination date
BA part:
separately for each treatment, ranging from administration time of study drug until administration time of next study drug dose or end of trial-termination date)

Please note that all AEs reported between start of trial drug administration and the last per-protocol contact will be considered on treatment (i.e. no follow-up period is considered in this trial).

Displays of AEs will be presented separately for the treatments described in [Table 6.1: 1](#) and [Table 6.1: 2](#). In the SRD part, the subjects in DG 8 and 9 will be handled separately, but counted only once in total.

Two types of AE displays will be provided in the report:

A) Section 15.3 (separate for SRD and BA part) and Appendix 16.1.9.2.8 (for ClinicalTrials.gov (separate for SRD and BA part) and EudraCT (SRD and BA part combined)) of the CTR displays:

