$$y_{km} = \mu + s_m + \tau_k + \varepsilon_{km},$$

where

y_{km} logarithm of response measured on subject m receiving treatment k ,
 μ the overall mean,
 s_m the effect associated with the m^{th} subject, $m = 1, 2, \dots, n$

τ_k the k^{th} treatment effect, $k = 1, 2$

e_{km} the random error associated with the m^{th} subject who received treatment k .

The difference between the expected means for test treatment (400mg high-fat breakfast) and reference treatment (400mg continental breakfast), $\ln(400\text{mg high-fat breakfast}) - \ln(400\text{mg continental breakfast})$, will be estimated by the difference in the corresponding Least Square Means (point estimate). Two-sided 90% confidence intervals based on the t-distribution will be computed. These quantities will then be back-transformed to the original scale to give the point estimator (geometric mean) and interval estimates for the ratio between response under test and response under reference.

The analysis will be accomplished by using the XPKISTAT macro, based on PKS (design BWU).

Investigation of relative bioavailability (BA part)

CTP: *Relative bioavailability is primarily to be determined on the basis of the parameters $AUC_{0-\infty}$ and C_{\max} [...]. Those parameters will be ln-transformed (natural logarithm) prior to fitting the model.*

The statistical model used for the analysis of $AUC_{0-\infty}$ and C_{\max} will be an ANOVA (analysis of variance) model on the logarithmic scale. This model will include effects accounting for the following sources of variation: 'sequence', 'subjects within sequences', 'period' and 'treatment'. The effect 'subjects within sequences' will be considered as random, whereas the other effects will be considered as fixed. For tests on subject, period, and treatment effects, the denominator sum of squares will be the sum of squares for error; while for tests on sequence effects, the denominator will be the sum of squares for subjects. The model is described by the following equation

$$y_{ijkm} = \mu + \zeta_i + s_{im} + \pi_j + \tau_k + e_{ijkm},$$

where

y_{ijkm} logarithm of response measured on subject m in sequence i receiving treatment k in period j ,

μ the overall mean,

ζ_i the i^{th} sequence effect, $i = 1, 2, \dots, 6$

s_{im} the effect associated with the m^{th} subject in the i^{th} sequence, $m = 1, 2, \dots, n_i$

π_j the j^{th} period effect, $j = 1, 2, 3$

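### Does the fixed order of breakfasts in dose groups 8 and 9 call for a change to the SAP's diet comparison?

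*SAP*

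**What the plan says.** Protocol Section 6.2.2 fixes the order. Subjects receive the trial medication "at first in DG 8 (Visit 2) following a standard continental breakfast and in DG 9 (Visit 3) following a high-fat breakfast". The footnote to the SRD flow chart describes "Two identical treatment periods separated by a wash-out phase of at least 14 days". Both groups receive 400 mg (protocol Table 4.1.4: 1).

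SAP Section 6.1 repeats the visit order and says the same subjects are "treated with the same treatments (i.e. always with active or with placebo) for an intra-individual comparison of the two different diets". Its Table 6.1: 3 lists high-fat as test and continental as reference, beside the two contrasts of the BA part.

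SAP Section 7.5.2 fits log AUC0-∞ and log Cmax with a random subject effect and a fixed treatment effect. It estimates "The difference between the expected means for test treatment (400mg high-fat breakfast) and reference treatment (400mg continental breakfast", back-transforms the difference and gives a two-sided 90% CI. The macro design is BWU, which SAP Section 2 expands as "Bioavailability/Bioequivalence, Within-Subject Design, Time-Uncontrolled". The BA part, described next, has six randomised sequences, terms for sequence and period, and design BWC, the time-controlled counterpart.

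The visible remark on time effects is in protocol Section 3.2: "As time-effects are expected to be small relative to the differences between the doses in the broad range investigated", unbiased comparisons can still be expected.

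**The concern.** The reason for treating the same subjects twice is to compare two diets. Because nobody takes the breakfasts in the reverse order, anything that differs between Visit 2 and Visit 3 enters the ratio in full, and the interval makes no allowance for it. Reading the ratio as a diet effect needs the assumption of no period effect, and SAP Section 7.5.2 does not write that assumption down.

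The protocol's remark on time effects does not fill the gap. It weighs them against differences between doses, and here the dose is the same on both occasions. Table 6.1: 3 also sets this contrast beside the BA contrasts with no sign that those are protected against period effects and this one is not. At stake is a diet conclusion that a reader might take as cleaner than the design allows.

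**Working it through.** **The plan's own figure.** Neither document gives a sample size or precision for this contrast, so there is none to reproduce. As a check on the variability inputs, the BA table in protocol Section 7.6 reproduces with half-width t(0.95, 20) × √ln(1+gCV²) × √(2/12) × √(χ²(0.95, 20)/20), which gives 0.175, 0.217 and 0.259 at gCV 20, 25 and 30%. The same conversion from gCV to log-scale SD is used below.

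**Inputs.** Six subjects on active drug (SAP 6.1), 90% two-sided CI (SAP 7.5.2) and gCV 20–30%. The gCV range is borrowed from protocol Section 7.6, because none is given for dose groups 8 and 9. The period ratios are assumptions; no document gives one.

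**Step 1: can a period term be fitted?** Six subject columns plus one treatment column have rank 7. Adding a period column makes 8 columns, but the rank stays 7, because period and treatment coincide in every subject. In a balanced two-order design the rank would be 8 of 8. Placebo subjects cannot supply the missing information, since the PKS is restricted to subjects treated with BI 730357 (SAP 6.3). Leaving period out is therefore the only option.

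**Step 2: what is estimated?** The mean within-subject log difference has expectation ln(diet ratio) + ln(period ratio). On the ratio scale, the estimate targets diet × period.

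**Step 3: how much could it matter?** SE = √ln(1+gCV²) × √(2/6) = 0.114, 0.142 and 0.170 at gCV 20, 25 and 30%. With 5 degrees of freedom t(0.95, 5) = 2.015. Coverage of the diet ratio is P(|T| ≤ 2.015), where T is noncentral t with noncentrality ln(period ratio)/SE. For a ratio of 1.10 the noncentrality is 0.0953/0.114 = 0.84 at gCV 20% and 0.0953/0.170 = 0.56 at gCV 30%.

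| Assumed period ratio | gCV 20% | gCV 25% | gCV 30% |
|---|---|---|---|
| 1.00 | 90% | 90% | 90% |
| 1.05 | 88% | 89% | 89% |
| 1.10 | 81% | 84% | 86% |
| 1.20 | 60% | 70% | 76% |

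Simulation agrees with these figures to within about 0.2 percentage points where it was run.

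**Step 4: what is already visible in the SAP?**
- Section 6.1 gives the visit for each breakfast.
- The model equation in Section 7.5.2 has subject and treatment only, while the BA equation directly after it has sequence and period.
- The design code is the time-uncontrolled one, against the time-controlled one for the BA part.

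A statistician reading these together sees that period is taken as null.

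**Step 5: what would a written assumption change?** The model, the point estimate, the SE, the interval and the macro call would all stay the same. The comparison has no hypothesis and no acceptance range. The preliminary PK data used before each escalation are individual values and geometric means of AUC0-24 and Cmax (protocol 7.3.4), not this ratio.

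**The case for a change.** The strongest argument for acting is that estimation is the whole aim here, so the plan should say what the estimate means, and a sentence costs almost nothing. The design code appears spelled out only in an abbreviation list; it names a design and states no assumption. The 14-day washout and the rule on predose values above 5% of Cmax (protocol 7.3.5) deal with carry-over, not with period effects in general. Amendment 3 says that the added fed groups are meant to inform on the influence of diet at higher doses and to support later development, so the ratio will be read.

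Much of this stands. The aliasing is complete, the assumption is not put into words, and the dose-based remark in protocol Section 3.2 does not reach a contrast at one dose. Three points weigh against a required change. Section 3.2 does name time effects as a disadvantage of the design, and the SAP (Section 3) presumes familiarity with the protocol. No mechanism for a drift of 10–20% is offered: the trial has one centre, the same procedures in both periods, and standardised meals and dietary restrictions. Barring any diet conclusion, or relabelling Table 6.1: 3, would go too far, because a reading conditional on no period effect is legitimate and is what the comparison was set up for. What the clinical trial report says about the ratio cannot be judged from these documents.

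**Conclusion.** The observation is correct, but it does not call for a change. The ratio and 90% CI for dose groups 8 and 9 estimate diet and period together and describe diet alone only if period has no effect. That limitation comes from the dosing order and cannot be repaired in the analysis. The SAP uses the right model for the order it has and shows the limitation through the visit order, the absent period term and the design code.

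What is missing is one interpretive sentence. Authors who wish to may add it, in the SAP or where the result is discussed, but its absence alters no number and no decision. The coverage losses in the table rest entirely on assumed period shifts and a borrowed gCV range; with no period effect the interval has its nominal 90% coverage. For an exploratory contrast in six subjects without an acceptance range, this is a gap that a competent analyst fills when interpreting the result.
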